6.3. Overview of Statistical Methods

An overview of the statistical methods for the HeartShare Deep Phenotyping Study are presented here. Full details of the statistical methods are available in the HeartShare Manual of Procedures.

- **Aim 1:** To identify novel diagnostic, physiologic, imaging, and molecular markers that differentiate HFpEF from non-HFpEF. We will use standard methods for evaluating differences between cases (HFpEF) and comparators without HFpEF, including t-tests (or non-parametric equivalent, when indicated) for continuous variables and Chi-squared tests (or Fisher exact tests, when indicated) for categorical variables. We will also use linear, logistic, and Cox regression analyses (as indicated), adjusting for potential confounders including multiple hypothesis testing, to examine for statistically significant differences between cases and comparators.
- **Aim 2:** To investigate the underlying pathophysiological and biological determinants of previously identified HFpEF subtypes. Here we will use standard statistical approaches, comparing the previously identified HFpEF subtype to all other HFpEF patients using approaches similar to Aim 1 above. We will follow-up these analyses by bioinformatics analysis including clustering of multi-omic data to determine whether specific molecules and biological pathways are over-represented in the previously identified HFpEF subgroup vs. other types of HFpEF patients and comparators.
- **Aim 3:** To identify and enable external validation of novel HFpEF subtypes using unsupervised machine learning of deep phenotyping data, images, and multi-omics. Several types of unsupervised machine learning (unbiased pattern recognition) approaches, alone or in combination, can be used in a variety of ways in HeartShare to identify and validate novel HFpEF subtypes. For example, unsupervised ML (e.g., Bayesian model-based clustering) can be performed on deep phenotyping data, followed-up by identification of molecular pathways underlying each HFpEF subtype using multi-omics approaches. Alternatively, unsupervised ML can be applied directly to multi-omics data, and differences in deep phenotyping indices among the identified HFpEF subtypes can be evaluated. We will test whether a multimodal precision medicine approach could identify distinct HFpEF subtypes using both deep phenotyping and multi-omics data simultaneously using innovative machine learning approaches that integrate a multiple data types, such as dual autoencoders for meta-embedding (Dual-GAME) and hybrid nonnegative matrix factorization (HNMF), as described previously.^{11,31-33}

6.4. Missing Data

Maximum efforts will be made to minimize missing data. When necessary, multiple imputation will be used to impute missing values in all variables included in the analyses.

7. PROTECTION OF HUMAN SUBJECTS

7.1. Potential Benefits

Participants may benefit from participation in the study as they will receive assessment of cardiovascular function and other organ function and information about their physical activity levels. With permission, these results can be shared with the participant's health care provider. Referrals to health care providers will be made, at the request of participants, in situations where participants do not have access to appropriate primary or specialty care. Study staff and if appropriate, physicians will respond to telephone calls from participants and their physicians regarding interpretation of the results provided.

7.2. Importance of Knowledge to be Gained

Understanding novel heart failure subtypes may result in advancements in precision medicine and targeted therapeutics for patients with heart failure.

7.3. Risks to Study Participants

7.3.1. Loss of Confidentiality

Only de-identified participant data are distributed for use in analyses. Participants will be distinguished by unique ID numbers that encode for clinic site. The key linking the participants' identifying information to their study number will be kept in protected files that require usernames, passwords and filenames and will exist only at the study site on a secure, encrypted computer.

7.3.2. Physical Examination

The physical examination procedures used in this study are low risk.

7.3.3. Questionnaires, Surveys, and Cognitive Testing

Questions may be sensitive in nature and may cause mental or emotional discomfort. Participants may refuse to answer any question that makes them feel uncomfortable.

7.3.4. Blood, Urine, Stool, and Saliva Sample Collection

Blood is drawn only by trained and experienced personnel via venipuncture and/or intravenous cannulation to minimize the discomfort and risks. Risks of drawing a blood sample are discomfort at the site of needle insertion, bruising, or inflammation at the site, and rarely, faintness or infection. Bruising, if it occurs, is usually painless and disappears within a few days. There are no known risks of urine, stool, or saliva sample collection.

7.3.5. Peripheral Arterial Tonometry

This procedure has no known risks other than a risk that during the 5 minutes when the blood pressure cuff is inflated, the participant may feel temporary discomfort.

7.3.6. Electrocardiography

The risks of electrocardiography can include skin irritation and a rash from the gel that is used or from wearing or removing patches that are used to conduct the measurements.

7.3.7. Arterial Tonometry

This procedure has no known risks other than temporary discomfort at the time of blood pressure cuff inflation.

7.3.8. Six-Minute Walk Test

Risks of this test include shortness of breath and chest tightness, and rarely, faintness or palpitations due to arrhythmias. We will guard against these by asking the participants questions before the test to determine whether it is safe for them to have this test. During the test, participants are closely monitored by study staff and the participant can stop and rest at any point during the test.

7.3.9. Short Physical Performance Battery (SPPB)

Risks of the SPPB include shortness of breath and rarely, lightheadedness or loss of balance. We will guard against these by asking the participants questions before the test to determine whether it is safe for them to perform this test. During the test, participants are closely monitored by study staff, and the participant can stop and rest at any point during the test.

7.3.10. Pulmonary Function Test

Participants may experience dizziness during the tests, coughing, feeling short of breath or feel lightheaded. These symptoms typically resolve shortly after the test is finished.

7.3.11. Cardiopulmonary Exercise Test

During exercise test, the patient may feel muscle soreness or fatigue, shortness of breath, abnormal blood pressure, or fainting. Rarely exercise can cause irregular heart rhythms, heart attack, stroke, or sudden cardiac death. Participants may become uncomfortable during the exercise test. It is expected that they will become tired and short of breath, and that the patient's blood pressure, heart rate, and other vital signs will change as a result of exercise. The risk of an adverse event occurring is the same or lower in the exercise laboratory as it would be if they exerted themselves elsewhere. Monitoring during exercise permits supervising staff to stop tests prior to when a patient may stop, which lowers the likelihood of an adverse event compared to the participants exercising at home on their own. Participants will be closely monitored throughout the entire period by individuals who are trained to respond if the aforementioned situations that might develop.

7.3.12. Cardiac MRI

During this test, participants will lie in a small, enclosed area inside a large magnetic tube. Some participants may be scared or anxious in small places (claustrophobic). The MRI scanner makes loud banging noises while taking a measurement, so either ear plugs or specially designed headphones will be used to reduce the noise. Participants who self-report claustrophobia will be excluded. Should a participant develop new claustrophobia or want the scan to be stopped for any reason, the technician will do so and remove the participant from the scanner.

The use of gadolinium-based contrast agents in patients who already have severely reduced kidney function (i.e., stage 4 or worse chronic kidney disease) is uncommonly (<0.07%) associated with a possibly fatal disease involving the skin, muscles, and internal organs. This disorder is called nephrogenic systemic fibrosis (NSF). Participants will have blood drawn to test their kidney function prior to the MRI and will be asked if they have any history of kidney problems. Deposits of gadolinium remain in the brain of some patients who have undergone MRI scans with gadolinium for a prolonged time after the last administration. Deposits of gadolinium have also been reported in skin and bone. The FDA determined that there is no evidence of long-term safety risk.

Metallic taste in the mouth, tingling in the arm, nausea, or headache occurs in less than 1% (less than 1 in 100) people. Insertion of the needle may also cause minor pain, bruising and/or infection at the injection site.

The dose and frequency of the contrast agent given to participants will be standardized. We do not expect any additional risk to be posed beyond those already described above. Participants

should avoid receiving additional gadolinium within 24 hours before or after the dose given in this research study.

7.3.13. Echocardiography

There are no known risks associated with using ultrasound waves to image the heart. Some individuals may experience some mild pressure, discomfort, and/or irritation from the transducer on the chest. The patient may also experience a cool or wet feeling from the gel applied to the chest. The risks of the exercise portion of the test are listed above in section 7.3.10.

7.3.14. Computed Tomography

The cumulative radiation exposure from the CT scan is considered small and is not likely to adversely affect the patient. However, the effects of radiation add up over a lifetime. It is possible that having several of these tests may add to a participant's risk of injury or disease. Before a participant decides to enter this study, patients will be asked about their past and future contact with radiation. Examples of contact with radiation include x-rays taken for any reason or radiation therapy for cancer treatment. The radiation exposure from one CT scan is approximately equal to 1.8 years of background radiation. The scan will be reviewed for findings that may have a major impact on the patient's health, such as cancer. These findings may cause worry, additional medical testing, and, potentially, cost.

7.3.15. Skeletal Muscle and Adipose Tissue Biopsies

The potential risks of the muscle tissue and fat tissue collection is a risk of pain from the local anesthesia, bruising and bleeding (hematoma), infection, cutaneous anesthesia from cutting a subcutaneous sensory nerve for the muscle tissue collection (<1%); the latter is almost always temporary but occasionally can become permanent. The procedures are well tolerated when performed by properly trained staff, which will be required for this study. Participants may be asked to stop or reduce their blood thinner(s) if they take them (for example, anti-platelet therapy or anticoagulation therapy) during the week leading up to a study muscle biopsy procedure. Stopping or reducing anti-platelet therapy or anti-coagulation therapy during this week may increase risk of a heart attack or stroke. These requests will be reviewed with the caring physician to minimize any risk. If risk is considered clinically unacceptable, the biopsy will be cancelled for medical reason.

7.3.16. Ambulatory Blood Pressure Monitoring

Wearing an ambulatory blood pressure monitor is considered to be low risk. The participant may feel some pressure when the blood pressure cuff inflates and may experience some discomfort while trying to sleep while wearing the cuff.

7.3.17. Genetic Research

The genetic research risks to participants are loss of confidentiality and re-identification. Prior to being included in any genetic research analysis, participants will have given written informed consent. To maintain participant confidentiality and to prevent genetic data from being linked to the identity of the participant, biospecimens will be deidentified prior to any genetic analysis. Only the collecting site will have the link between associated PHI and the genetic samples. Each site will store this linking information in a secured environment with restricted access.

7.4. Adequacy of Protection Against Risks

Approval to proceed with the HeartShare deep phenotyping protocol will be sought from the Institutional Review Board (IRB) at each study site. We anticipate this to be a low to moderate risk observational study. Participants for this study will be provided with an Informed Consent document, and written consent will be obtained from each participant prior to enrollment. We will follow existing Health Insurance Portability and Accountability Act (HIPAA) privacy regulations

with regards to personal health information. The investigators of this project will not utilize study data to identify specific persons.

8. REGULATORY CONSIDERATIONS

8.1. Institutional Review Boards (IRBs)

After approval by the HeartShare Steering Committee (comprised of the HeartShare Steering Committee Co-chairs, NHLBI program staff, and principal investigators of the HeartShare Data Translation Center and Clinical Centers) and the HeartShare Observational Study Monitoring Board, the Principal Investigator of the HeartShare Data Translation Center will submit this protocol to the IRB of record and will forward to the NHLBI a copy of the written and dated approval by the IRB. Clinical Center PIs will submit reliance agreements at their sites to their local IRBs to get approval for the study. The study (study number, protocol title and version number), the documents reviewed (protocol, informed consent form, and other study-related materials such as recruitment tools) and the date of the review will be clearly stated on the written IRB approval letter. During the study, any amendment or modification to the protocol will be sent to the IRB for approval. The IRB will also be informed of any event likely to affect the safety of participants or the continued conduct of the study, in particular any change in safety and all updates to the protocol will be sent to IRB.

8.2. Data Management, Confidentiality, and Ownership of Data and Biospecimens

All data and biospecimens will be maintained in secure locations. Data and biospecimens collected from study evaluations will be identified by study identification codes. Identifying features, including names and addresses will be known to the clinical center, but will not be provided to the Data Translation Center at Northwestern University. The study will be conducted in compliance with applicable International Council for Harmonization (ICH) guidelines, the ICH E6 Good Clinical Practice guideline, and regulations, guidelines, and applicable laws of the local site where the study is conducted. The study will be conducted with the approval of a duly constituted IRB in accordance with the requirement of US regulation Title 21 Code of Federal Regulations (CFR) Part 56-Institutional Reviews Boards. The nature and risks of the study will be fully explained to each participant, and written consent obtained in accordance with the requirements of 21 CFR 50-Protection of Human Subjects. Participants will be informed of their rights, including the right to withdraw from the study at any time.

Use of study data and biospecimens, and resulting findings, during the HeartShare study are subject to approval of the HeartShare Steering Committee and must follow guidelines of the HeartShare Publications and Ancillary Study Committee. The data and biospecimens from participants at the HeartShare Clinical Centers are the property of the HeartShare study and are under the custody of the enrolling center.

8.2.1. Data Security

The consent form signed by the participant will provide written assurance that all individual data collected in the study will be kept confidential to the extent provided by the Privacy Act of 1974 and by the Health Insurance Portability and Accountability Act (HIPAA). Each center which has data with personal identifiers will provide file security so that confidential data are not released. Specifically, participants will be informed that: (1) the only people who will know that they are research participants are members of the research team, authorized members of the workforce at the clinical center and, if appropriate, their physicians or health care providers; (2) no individual identifying information about them will be disclosed to others, except as part of ascertainment of events information, as permitted by the consent form, or if required by law; and (3) when the results of the study are published or discussed in conferences, no information will be included that would reveal their identity. All research staff at the Data Translation Center and

at each site will be required to provide proof of biomedical research training (e.g., CITI certification) prior to conducting any study-related procedures. All data will be password protected and encrypted at each site, and at the Data Translation Center. Authorization of access to all study-related data will be provided by each site principal investigator (for data that resides at the site) and by the Data Translation Center (for all data that resides centrally).

8.2.2. Quality Control

All study procedures and data will undergo quality control and quality assurance as outlined in the central core laboratory Manual of Procedures for each central core laboratory for each study procedure. In general, steps to ensure quality control include (1) central training of site staff conducting each procedure; (2) a checklist to ensure study procedure completeness that each core laboratory completes upon receipt of studies; (3) feedback to sites when quality of submitted studies is sub-optimal; (4) corrective action plan for sites who do not meet quality control metrics; and (5) assessment of inter- and intraobserver variability, and measurement drift, at regular intervals throughout the study at each core laboratory.

Quality assessment of data transmitted from sites to the Data Translation Center HeartShare REDCap database will be conducted using multiple methods. Sites will be asked to confirm whether the summaries provided are consistent with summaries they generate using their native data sets. Discrepancies will be resolved in monthly phone calls and formally tracked in a change log for each cohort and variable. These summaries and graphical displays will also be used to identify outliers and potential errant values. Range, logic and consistency checks will also be programmed, run and reviewed for all harmonized variables. The second approach to quality assessment of harmonized data will be via upload to an internal quality assessment REDCap database established expressly for purposes of harmonization. Data dictionaries will be independently constructed in the REDCap environment to complement the developed CDEs. When data harmonization for a subset of variables has been completed by the HeartShare Data Management Core and reviewed by contributing sites, bulk upload of the data for these variables to REDCap will be attempted. If values remain in the harmonized data set that do not comply with the data dictionary, e.g. if a categorical variable has values that are not included in the REDCap data dictionary, data upload will fail and errors will be noted. This approach will provide an independent check of successful harmonization across all cohorts. Furthermore, the REDCap data dictionary will provide a straightforward approach to streamlining CDM/CDEs for distribution through the HeartShare Data Portal.

8.2.3. Data/Specimen Handling

The data and biospecimens are transmitted to the HeartShare Data Translation Center (or designee) and cannot be moved to another institution unless approved by the HeartShare Steering Committee; for example, if the Principal Investigator of the center moves to another institution. At the conclusion of the HeartShare study, the data and remaining biospecimens will be transferred to a HeartShare-specified biobank and/or to the NHLBI Biological Specimen and Data Repository Information Coordinating Center (BioLINCC) biobank and will become the property of one of these organizations. Future researchers may request data or biospecimens from a biobank with approval following the guidelines of the biobank. Only study identifiers (and no personal health information) will be included with deposited data and specimens. Data will be stored at the Data Translation Center and in BioData Catalyst. Specimens will be stored at the HeartShare biospecimen core laboratory at the University of Vermont. Data and specimens will be stored indefinitely. Only investigators approved by the Data Translation Center will have access to data and specimens. Site staff are responsible for transmission of data and specimens; the Data Translation Center staff (or designee) will be responsible for receipt of data and specimens. Data will only be transported electronically using secure, encrypted methods. Specimens will be shipped by standard shipping service providers.

Very detailed (de-identified) information about participants' genetic information will be stored centrally in the secure NHLBI BioData Catalyst computing resource, where it will be shared with other investigators for research. This information and all of participants' other data will be used by researchers to look for genes that provide better understanding of why heart failure develops and how it can be better treated. The stored information is de-identified, which means that identifying information such as the participant's name, date of birth, address, etc., is removed. The HeartShare Data Translation Center will control access to this stored information. The Data Translation Center is committed to protecting the confidentiality of all the information it receives, but will also comply with relevant laws, which might include Freedom of Information Act (FOIA) requests for deidentified information. Other researchers that are not part of HeartShare may request access to these de-identified samples or data. This access is handled by the Data Translation Center according to approved policies and procedures.

8.3. Informed Consent

See Section 3.4 above for details about the informed consent process. The site investigator, or a person designated by the site investigator, will fully inform the participant of all pertinent aspects of the study including the review of the IRB-approved informed consent form. All study procedures and potential risks will be discussed in detail with each participant. The Informed Consent Form (eConsent) will be signed and personally dated by the participant prior to the commencement of any study procedures. All participants will receive a copy of the informed consent form. Non-English speaking consent forms will be made available as needed. Electronic copies of the signed eConsent forms will be retained at each study site.

8.4. Adverse Events

All adverse events occurring within the HeartShare study evaluations (baseline or other visits) will be recorded and reported, starting at the beginning of the Deep Phenotyping baseline visit, and continuing for a 48 hour period after the in person testing has been completed. For patients participating in multiple in person study visits (e.g., for optional biopsy procedures or annual follow up visits), adverse events occurring during the 48 hours following each testing epoch will also be evaluated for and reported.

- **Adverse event:** An adverse event (AE) shall be considered any detrimental change in the patient's condition.
- **Anticipated adverse event:** Anticipated adverse events are defined for each of the protocol procedures in the sections specifically written for those procedures.
- **Unanticipated adverse event:** Any adverse event that results in risk or harm to the participant or others that differs from the known, predicted possible effects of the research protocol. An unanticipated adverse event is one that varies in nature, intensity, or frequency from information in the informed consent document.
- **Serious adverse event:** Any event that results in death, inpatient hospitalization or prolongation of existing hospitalization, a persistent or significant disability or incapacity. Important medical events that may not result in death, be life-threatening, or require hospitalization may be considered a serious adverse event when, based upon appropriate medical judgment, they may jeopardize the patient or participant and may require medical or surgical intervention to prevent one of the outcomes listed above.
- **Monitoring of adverse events related to the study:** The occurrence of an AE may come to the attention of study personnel during study visits or telephone interviews or by a patient presenting for medical care. The AEs that are expected from participation in the study are given in the consent form.

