5. STUDY PROCEDURES

5.1. Study Visits

Once consented, all study participants will undergo a 2-day baseline visit. Depending on the scheduling systems, physical location, and availability of the various tests required for the study, centers may split each of these visits into more than 2 days or rearrange the order of procedures, but in all cases, the duration of testing will closely approximate the details in **Table 1**. The in-person and remote data collection components of the baseline visit must occur within

a 30-day window. Thereafter, participants will receive two short surveys monthly and several longer surveys every 6 months via Eureka (see Supplementary Tables 2 and 3).. Participants will return to the Clinical Center for an in-person follow-up visit one year after the baseline visit. The one-year follow-up visit will be much shorter than the baseline visit. 2 lists the schedule of events (all components of the deep phenotyping study visits and and remote data collection instruments).

Table 1. Duration of Deep Phenotyping Study Components

Duration	Study component
Prior to baseline visit	
20 minutes	eConsent (to be done in person for participants who request it)
30 minutes	Telephone survey for medication reconciliation and medical history (in person if no prior eConsent)
Day 1 (begin fasted)	
15 minutes	Blood & urine
30 minutes	EndoPAT (peripheral arterial tonometry)
30 minutes	12 lead ECG, vitals, waist and hip circumference
30 minutes	Snack
30 minutes	Pulmonary function tests
20 minutes	Arterial tonometry (for arterial stiffness and pulsatile hemodynamics assessments)
90 minutes	Cardiopulmonary exercise testing + echo (rest + exercise)
30 minutes	Eureka questionnaires (if not done prior the study visit)
30 minutes	Education on Eureka, Kardia, and 24-hour BP devices and remote study procedures and geolocation + light lunch
Day 2	
15 minutes	6-minute walk test
60 minutes (scan time 15 minutes)	CT (chest, abdomen, thigh)
120 minutes (scan time 60 minutes)	Cardiac MRI
25 minutes	Cognitive testing
10 minutes	Short Performance Physical Battery
60 minutes	Lunch
90 minutes	Skeletal muscle biopsy (optional), adipose biopsy (optional)

Total time for Day 1: ~5 hours

Total time for Day 2: ~3 hours, 45 min (total time = ~5 hours, 15 min with optional biopsies)

Table 2. Schedule of Events

Assessment/Activity	Baseline	Monthly surveys via Eureka	6-month surveys via Eureka	12-month Follow-up visit* (In-Person)
In Person Visits				
eConsent	(X)			

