5.2.18. Tissue Biopsies (optional)

Patients who take blood thinners (for example, warfarin or novel oral anticoagulants) may be asked to stop or reduce these medications during the week leading up to a tissue biopsy procedure. For both muscle and adipose tissue collection, participants will be given printed instructions on how to prepare for the day of the tissue collection and how to care for the collection sites after the procedure. Follow-up phone calls will be made approximately a week after the procedures to assess healing of the collection sites.

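### The adverse event window in Section 8.4 leaves out most of the pre-biopsy blood-thinner week, where Section 7.3.15 places a heart attack or stroke risk, and site events that first arise after 48 hours

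*Protocol*

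**What the plan says.** Section 8.4 fixes when an adverse event must occur to be recorded and reported. The window opens "starting at the beginning of the Deep Phenotyping baseline visit" and closes after "continuing for a 48 hour period after the in person testing has been completed". For participants with more than one in-person visit, with optional biopsies given as an example, "adverse events occurring during the 48 hours following each testing epoch will also be evaluated for and reported". Section 8.4 also takes its anticipated adverse events from the sections written for each procedure. For biopsies, that risk section is 7.3.15.

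Two other places describe the biopsy period:

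- **Before the biopsy.** Section 5.2.18 says that participants on blood thinners "may be asked to stop or reduce these medications during the week leading up to a tissue biopsy procedure". Section 7.3.15 gives the consequence: "Stopping or reducing anti-platelet therapy or anti-coagulation therapy during this week may increase risk of a heart attack or stroke".
- **After the biopsy.** Section 7.3.15 lists site harms, among them "bruising and bleeding (hematoma), infection" and sensory nerve injury, without onset times. Section 5.2.18 adds: "Follow-up phone calls will be made approximately a week after the procedures to assess healing of the collection sites".

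Table 1 in Section 5.1 puts the optional biopsies last on Day 2 of the two-day baseline visit. The same section lets centers spread the visit over more days, with the baseline components falling within 30 days.

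**The concern.** By reference to 7.3.15, Section 8.4 in effect accepts heart attack or stroke after a requested blood-thinner change as an anticipated adverse event. It then sets a start time that, on the default schedule, comes after most of the week in which that risk is placed. A site that follows 8.4 to the letter would have no duty to record such an event as an adverse event, although the study's own request may have contributed to it.

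The end of the window raises a smaller question. The study already telephones participants about a week after the biopsy to ask about healing, but the window has closed about five days earlier. A wound infection that begins on day 4 would be heard of at that call and yet not be a reportable adverse event.

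At stake is the completeness of safety information on the optional biopsies. The scientific aims are not affected.

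**Working it through.** The protocol gives no figure to reproduce. The check lays the window over the biopsy timeline.

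**Inputs.**
- Window start, and window end at 48 hours (2 days): Section 8.4.
- Possible blood-thinner change: up to about 7 days before the biopsy (5.2.18, 7.3.15). A full 7 days is an assumption, because the text says only that participants may be asked to stop or reduce.
- Healing call: about 7 days after the biopsy (5.2.18).
- Biopsy on Day 2 by default: Table 1.

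**Before the biopsy** (days outside = 7 minus days inside the window).
- Biopsy on Day 2 of a consecutive visit: the window opened about 1 day earlier, so 7 − 1 = 6 days lie outside.
- Separate biopsy visit, using only the sentence on testing epochs: that window starts after the testing, so 7 − 0 = 7 days lie outside. A participant who has a stroke in that week and never reaches the biopsy has no biopsy epoch, so no biopsy window opens.
- Split baseline visit, biopsy at least 7 days after its start, window read as running unbroken to 48 hours after all in-person testing: 7 − 7 = 0 days lie outside.

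**After the biopsy.** Days inside: 2. Days outside, up to the call: 7 − 2 = 5 (days 3 to 7).

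**Together, over 7 + 7 = 14 days.**
- Day 2 schedule: 6 + 5 = 11 outside; 11/14 = 79%.
- Separate visit, epoch sentence only: 7 + 5 = 12 outside; 12/14 = 86%.
- Continuous reading of a split baseline: 0 + 5 = 5 outside; 5/14 = 36%.

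These are shares of calendar days. They are not shares of events missed, since harms need not be spread evenly over the days and the protocol gives no onset distribution. For a participant with no blood-thinner change, only the post-biopsy part applies.

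**Occurrence or detection.** The 48-hour limit in 8.4 concerns when an event occurs. The same section names telephone interviews as one way an event may come to notice. An early hematoma, or a nerve cut at the incision, is therefore reportable even if first heard of at the one-week call. Only events that first arise after 48 hours are left out.

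**Scope.** Section 5.2.18 ties the blood-thinner request to any tissue biopsy and gives anticoagulants as examples. Section 7.3.15 ties it to the muscle biopsy and names antiplatelet drugs as well. The two need reconciling, because they define whose pre-biopsy week is at issue.

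**The case against.** The strongest case on the other side has four parts.

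- **The window may be wider than it looks.** The sentence on separate visits adds to the baseline sentence and does not replace it. If the baseline visit is split and its window is continuous, the blood-thinner week can lie wholly inside. This stands as a possible reading, but capture would then depend on local scheduling. It does not help on the default Day 2 schedule.
- **Serious events have other routes.** Hospitalizations are surveyed at baseline and monthly (Table 2). Deaths and cardiovascular hospitalizations are centrally adjudicated (5.3.1). The IRB is told of events likely to affect participant safety, with no time limit stated (8.1). It would therefore be too strong to say that a stroke in that week goes unrecorded. These routes do not, however, link an event to a study procedure, and a wound infection treated without admission is not among the events listed in 5.3 and 5.3.1.
- **The risk is limited beforehand.** Blood-thinner requests are reviewed with the treating physician, and the biopsy is cancelled if the risk is unacceptable (7.3.15). That may lower the risk, but it does not record harm that occurs.
- **The group is small.** Biopsies are optional and done in a subset, and only some of those participants take blood thinners. This stands, and it limits the weight of the point.

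A reader might also infer that the protocol itself places harm in the week after the biopsy, or that the monitoring board will be shown a complication rate that is too low. The text supports neither. Section 7.3.15 gives no onset times for site harms, and 5.2.18 only schedules a call. Section 8.7 describes no biopsy complication rate and refers to a charter that is not part of the protocol.

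**Conclusion.** The mismatch is real and worth correcting. On the default schedule about 6 of the 7 pre-biopsy days, to which the protocol explicitly attaches a risk of heart attack or stroke, precede the adverse event window. For a separate biopsy visit the number outside runs from 0 to 7, depending on scheduling and on how 8.4 is read; that ambiguity is itself a defect. After the biopsy, about 5 days before the healing call are uncovered, and only for events that first arise in them.

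This rests on a blood-thinner change lasting the full week and on the call being made at about day 7. The number of events involved cannot be estimated from the protocol. The pre-biopsy gap is the firmer part, because the protocol states the risk and its timing. The post-biopsy gap is inferred from the healing call and the untimed list of site harms.

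**What to change.** Reconcile Section 8.4 with 5.2.18 and 7.3.15, for biopsy participants only:

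1. Open adverse event recording when the participant is asked to change a blood thinner, or at the visit if no change is requested.
2. Close it at the existing one-week healing call, and record that call on the adverse event form.
3. Say whether the baseline window is continuous when a center splits the visit.
4. Summarize pre-biopsy events over all participants asked to change a blood thinner, whether or not the biopsy took place, and site events over biopsies performed. The number of biopsies alone would be the wrong denominator for the pre-biopsy risk: it drops anyone whose event prevented the biopsy.

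The cost is amendment wording, an added form entry at a call already planned, and slightly more adverse event reports. No change to any blood-thinner rule or other clinical rule is proposed.
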